VA Office of Research and Development Results Record C0239-R

Title: Randomized Trial Comparison of Ototoxicity Monitoring Programs

ClinicalTrials.gov identifier: NCT02099786

Protocol; Document Date: 9-29-17

Experimental Methods

A. Subjects.

A1. Subject Recruitment: An estimated 320 patients from VA Portland Health Care System (VAPORHCS) receiving chemotherapy will be identified by a search of the upcoming chemotherapy unit appointment list, pharmacy list or by oncology referral including verbal referral and encrypted email. Additionally, approximately 120 healthy control subjects (Veterans and non-Veterans) not administered chemotherapy will also be recruited at the VAPORHCS from posted recruitment advertisements and from the NCRAR database of Veterans willing to participate in future hearing research projects. Potential chemotherapy patients will be accessed using electronic medical records (CPRS) to determine the diagnosis and treatment plan and to search for exclusionary criteria. If the potential subject is not excluded based on initial CPRS search, oncology personnel will approach the potential subject to determine his/her willingness to learn more about the study after hearing a brief description. The Program Evaluation (PE) audiologist will then talk with the patient, offer a more thorough explanation of the study, including the necessity for duplicate testing. If the potential subject remains interested in the project, informed consent will be obtained including an explanation of the goals of the study, requirements of the study protocol and the potential risks and benefits to the subject.

Initial testing to establish inclusion in the study and to provide the first PE will be done in a quiet area. After the evaluation, if the subject has met all further inclusion criteria, the subject will be randomized to a treatment arm: Standard of care (SOC) or Comprehensive Ototoxicity Monitoring Program for VA healthcare (COMP-VA). Study personnel will then be informed that a subject has been consented, tested, and assigned to a study arm and is ready to receive a baseline evaluation.

A2. Subject Exclusion Criteria: Subjects must be treated for cancer and must provide a reliable hearing test to be enrolled in the treatment arms of this study. Criteria for excluding subjects (chemotherapy and controls subjects) from this study are: 1) cognitively or physically unable to participate (patient or nurse report patient is incapable of participating), CPRS indication that subject exhibits aggressive behavior, subject has documented dementia, Alzheimer's disease, or severe psychosocial disorder, CPRS notes indicate individual is not legally capable of providing informed consent (subject has a legal guardian); 2) exhibits Meniere's disease or retrocochlear disorder based on hearing test results, patient report or notes in CPRS; 3) exhibits active or recent history of middle ear disorder based on otoscopy, tympanometry, patient report, or notes in CPRS; 4) unwilling to participate; and 6) hearing thresholds > 70 dB SPL at 4 kHz and below (control subjects only).

B. Experimental Techniques. Study measurements are divided into three general groups: Program Evaluation measurements, SOC measurements (Arm 1) and COMP-VA measurements (Arm 2). Measurements in non-clinical controls generally mirror those done for the COMP-VA arm. Testing is done by an Audiologist. The SOC protocol (Arm 1: SOC) is done according to the Audiology Service established protocol. The COMP-VA (Arm 2) protocol includes hearing testing at baseline and at each treatment interval along with a one-month post-treatment evaluation. Testing will be done using OtoID and/or the OtoID-Tablet and/or a standard audiometer. As part of this project, we have developed an updated version of the OtoID which involved migrating to a tablet-controlled device. Like all audiometers, this audiometer is not a medical device since it is "non-invasive" and, therefore, does not require FDA oversight or approval. Rather, the OtoID-Tablet properties are defined and calibrated according to the American National Standards Institute (ANSI) S3.6-2010 "Specification for Audiometers". It was calibrated in 2017 and will be calibrated annually, per ANSI standards.

B1. PE and Longitudinal Follow-up Measurement: Program Evaluations will be completed in a quiet area and include 1) otoscopy; 2) tympanometry; and 3) hearing threshold testing and 4) the audiologist can elect to include DPOAE testing at any session. Various questionnaires will be given at the discretion of the audiologist. A study team member may request a patient's feedback in the form of a set of mostly open ended questions (Patient Interview Form). A phone call from PE study personnel will be made at regular intervals to inquire about the subject's general well-being, to determine if the

Veteran has experienced any recent noise exposure and retains adequate hearing protection, to ensure that contact information is accurate and not likely to change in the near future, and to remind the Veteran that study personnel will require a final hearing testing session (PE #3). The Veteran may be asked if he/she received any audiological care since the previous contact and requested to bring a report from this contact to the final (longitudinal) program evaluation. Subjects consented and tested may receive a longitudinal follow-up program evaluation depending on their randomization date.

B2. General Procedures for Ototoxicity Monitoring: Attempts will be made to establish baseline results within approximately 24 hrs of treatment. Results from the baseline test will be compared to all subsequent testing for the purposes of ototoxicity detection. Subjects will be provided with education about their hearing, potential changes in hearing and tinnitus associated with ototoxicity and the increased vulnerability of their auditory system to excessive noise exposure for at least a 1-year period after treatment. Disposable-type hearing protection is readily available to subjects at the VA Audiology Clinic and NCRAR.

B2a. Monitoring Procedures for Standard of Care (SOC): Hearing testing will be done according to their established protocol for ototoxicity monitoring in the Audiology Clinic.

B2b. Monitoring Procedures COMP-VA: COMP-VA hearing testing is done primarily using the OtoID and/or the OtoID-Tablet and/or a standard audiometer. *Baseline and monitor* testing may include: 1) otoscopy; 2) tympanometry; 3) pure tone air-conduction threshold testing; 4) DPOAE testing and 5) questionnaires. If the test results suggest a hearing change or that the Veteran is unable to complete the self-test, the subject may complete additional testing. Results will be entered into a CPRS progress note. A verified hearing change will be reported with oncology medical staff. Approximately one month after treatment ceases, subjects will be evaluated using procedures described above. The questionnaires may be given at each visit.

B3a. DPOAE measures for SOC: DPOAE measurements will be done according to their ototoxicity monitoring protocol.

B3b. DPOAE measures for COMP-VA: Testing will be done by study personnel in a quiet area.

B3b1. Baseline measurements COMP-VA: This testing may be done following the hearing test. Further testing is reserved primarily for those instances when the patient cannot take a reliable hearing test though the audiologist may elect to include DPOAE testing when time permits.

B4. DPOAE Reference Limits Testing on non-Clinical Control Subjects: 120 healthy control subjects will have their hearing and DPOAEs measured serially. Subjects must meet all established exclusionary criteria. Subjects will be tested approximately 6 times over the course of about 3 to 6 months. The variability in the numbers of tests and time frame is to allow our testing regimen to mimic several different cancer therapy regimens. In addition to DPOAE testing, protocol includes: Otoscopy, tympanometry, and hearing testing. Testing of control subjects will be done in a quiet area.

C. Instrumentation.

C1. Behavioral Testing Instrumentation for SOC: Equipment and space used for testing at the VAPORHCS Audiology clinic will be used for SOC. Equipment undergoes full calibration annually.

C1a. Behavioral Testing Instrumentation for COMP-VA: The OtoID audiometers (OtoID and OtoID-Tablet) are calibrated annually with level checks done at least monthly.

C2. Distortion Product Otoacoustic Emission Instrumentation for SOC: Distortion-product otoacoustic emission testing is currently accomplished using commercially-available equipment.

C2a. Distortion Product Otoacoustic Emission Instrumentation for COMP-VA: Either the OtoID-based DPOAE testing (or cart system) can be used to collect DPOAEs.

C3. Other data to be gathered on study participants with cancer: Additional information obtained on each subject from the electronic medical records (CPRS) will be entered into the database, maintained by by study team members including a biostatistician and research assistant(s). Information to be obtained will include patient factors such as name, gender, age, type of cancer and staging, drug treatment variables such as cisplatin dose and dosing (intensity) and concomitant radiation dose and doublet medication and other information related to treatment and patient factors as required to accomplish the study goals. CPRS clinical progress notes will be monitored by a study team member on each subject (estimated n=80/yr) entered into either study arm in order to obtain Audiology Service utilization **for up to one year** post-randomization. In addition, in order to get a less biased estimate of audiological services utilization rates, an historical cohort comprised of all patients identified as receiving cisplatin approximately 3 years prior to the initiation of the study will be searched in CPRS and the cancer registry for audiological services used (estimated n=220 pts). We estimate approximately 300 patient records may be accessed to complete this search. These data may be combined with data from other studies done by these investigators in an IRB-approved manner.

A study team member may request providers' feedback in the form of a simple checklist (Oncology Practitioner Survey) provided to them at each treatment interval by a study team member.

We may also survey practitioners (oncologists, nurses, and audiologists) to assess their beliefs about ototoxicity monitoring practices using an anonymous beliefs questionnaire (i.e., no PHI or PII). This survey will be made available at 2 intervals.

In order to establish a benchmark for relapse-free survivorship from which to compare COMP-VA subjects' survivorship, we will be evaluated survivorship of Veterans with a diagnosis of cancers treated with cisplatin using the VA Cancer Registry (or other) which follows Veterans treated in VA for 5+ years following treatment. We will follow current study participants for cancer survivorship for approximately 2-3 years depending on enrollment date and resources available to do so.

D1. Reporting Methods: All study related data are confidential and will be kept in secured locations at the NCRAR, Chemotherapy Treatment Unit 6C of the hospital, and the Audiology Clinic using password protected computers, locked offices, and cabinets in locked offices. The oncology medical personnel will be notified verbally and/or via CPRS notes if behavioral hearing threshold shifts meet or exceed criterion levels. Communication with oncology may occur in 2 ways: oncology study personnel may be sent a secure encrypted and restricted Outlook email to view indicating the subject number and name of the subject in order to find previous testing stored in the OtoID. The subject number is important since the data (hearing test results) stored on the OtoID contains only de-identified information including subject numbers and no patient identifiers. In addition, a lock-box containing a copy of the key that links the study subject name and the study number may be stored on the Chemotherapy Unit in the medication room (Rm 6C-157). This medication room is locked at all times and is only accessible to oncology medical personnel. This lock box is password protected with only IRB-approved study team members given the code. The study personnel nurse will be instructed to delete any email after use. Electronically-stored data will be kept at: **S:NCRAR/[name]/COMP-VA**, including the linking key between the PII and the data, all of which are password protected.

Once the study is completed, our intent is to bank all data collected under this approved study protocol if the subject allows (through written informed consent) the information collected to be added to a repository. This study will contribute samples to the "Data Repository for the Normal and Abnormal Functioning of the Auditory System, PI: [name] MIRB# 3589" located at the VAPORHCS for future use. If the subject opts out of the data repository, hard copies of data including identifiable data will be kept per IRQ (11-26-14) in a locked cabinet in a locked room (**P5F-189**) at the NCRAR and/or in a locked desk in a locked room (**1D-116a**) the Audiology Clinic.

E. Early Exit: Exit from study will occur if the Veteran 1) moves and will not live within proximity to permit continued participation; 2) elects to withdraw from the study; 3) fails to meet study protocol requirements.

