2. *We hypothesize that COMP-VA will minimize some of the adverse effects of cisplatin treatment on Veterans' hearing-related quality of life, either through treatment modifications to diminish cisplatin-induced hearing loss or effective post-chemo audiological service delivery to limit the ill-effects of any pre-existing, new or worsened communication deficit.* We will conduct a contrast of perceived hearing handicap (HHIE or HHIA questionnaire administered at 1 year post-randomization), between patients randomized to COMP-VA and SOC. We will conduct a t-test with randomization arm as the contrast to test the importance of COMP-VA on perceived quality of life outcomes.

3. *Compared with patients randomized to SOC, patients randomized to COMP-VA will use Audiology rehabilitation services at a higher rate because of their greater awareness of new, increased or pre-existing communication deficits.* To test this hypothesis, we will contrast the probability of one or more audiology clinic rehabilitation visits using logistic regression with group membership as a factor.

4. *We anticipate that cisplatin patients given the COMP-VA intervention will fair no worse than SOC patients in terms of their survival.* This component of the study is framed as a non-inferiority trial. i.e. we require sufficient evidence to reject the null hypothesis that COMP-VA patients have lower one-year survival rates than patients treated under SOC. Analysis for non-inferiority trials using survival outcomes have been described and are easily computed using logistic regression output. We will require a non-inferiority margin of no more than 1.1 mortality odds among COMP-VA patients relative to SOC patients. From an analytical

perspective this means that the upper 95% confidence bound for the fitted odds ratio must be less than 1.1 to reject the null hypothesis that COMP-VA induces extra mortality risks.

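### Do SAP hypotheses 2 and 4 make cisplatin claims about a randomised population that the Protocol does not restrict to cisplatin?

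*Protocol*

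**What the plan says.** Protocol A1 gives the source of patients as "An estimated 320 patients from VA Portland Health Care System (VAPORHCS) receiving chemotherapy". Staff look in the medical record "to determine the diagnosis and treatment plan and to search for exclusionary criteria", and randomisation follows "if the subject has met all further inclusion criteria"; no separate list of those criteria appears. A2 contains the one positive rule for the arms: "Subjects must be treated for cancer and must provide a reliable hearing test to be enrolled in the treatment arms of this study". Its exclusions concern capacity, ear disease, willingness and, for controls, hearing level. None concerns a drug, and the numbering skips an item: "4) unwilling to participate; and 6) hearing thresholds".

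In the SAP section on hypotheses, item 2 states that "COMP-VA will minimize some of the adverse effects of cisplatin treatment on" hearing-related quality of life in Veterans, and tests this with a t-test between the randomised arms. Item 4 opens by naming cisplatin patients in the COMP-VA arm. It then states its null hypothesis for COMP-VA against SOC patients without a drug, with an odds-ratio margin of 1.1. Items 1 and 3 name no drug.

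Protocol C3 collects cisplatin dose and intensity, concomitant radiation and doublet medication on participants with cancer. It also describes "an historical cohort comprised of all patients identified as receiving cisplatin approximately 3 years prior to the initiation of the study", and a registry benchmark for "survivorship of Veterans with a diagnosis of cancers treated with cisplatin".

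**The concern.** Read literally, the entry rule admits any patient treated for cancer, while two of the four hypotheses speak of cisplatin. If patients on other drugs were randomised, a quality-of-life or survival conclusion worded for cisplatin would rest on a mixed group. This matters most for hypothesis 4, which is a safety claim tested for non-inferiority. If COMP-VA caused harm only in cisplatin patients, for example through changes to their treatment, the presence of other patients would pull the odds ratio towards 1 and make a pass easier. The cisplatin historical cohort and survival benchmark in C3 would then also match only part of the randomised patients.

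**Working it through.** The question is mainly one of reading, so the texts are set side by side first.

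1. **Entry text.** A1 says chemotherapy and A2 says treatment for cancer. Taken literally these already differ, since cancer can be treated without chemotherapy, so both look like loose general terms. My reading is that the A2 sentence separates patients in the arms from the 120 healthy controls covered by the same list. Neither term excludes a cisplatin requirement, and neither states one.
2. **Hypothesis 4.** The drug is named once, for the COMP-VA side. In that same sentence the comparator is simply the SOC patients, although a like-for-like comparison must be meant. The null hypothesis then shortens both sides. The natural reading is abbreviation, not a second population.
3. **Hypothesis 2.** Cisplatin describes the harm to be reduced. The test itself is between patients as randomised. One of its two routes, better audiological care for a communication deficit of any origin, does not depend on the drug.
4. **C3.** The variables collected on the trial's own participants fit cisplatin-based treatment. They are given as examples, so this supports the reading without proving it. The historical cohort and registry benchmark are external groups, and neither enters any SAP test.
5. **Completeness.** Further criteria are mentioned but not listed, and item 5 of A2 is absent. The posted text cannot show whether a cisplatin criterion existed.

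**Validity of the contrast.** Let f be the share with planned cisplatin, and let d_c and d_o be the arm differences in mean score for cisplatin and other patients. Randomisation makes f equal between arms in expectation, so the all-randomised contrast estimates f·d_c + (1 − f)·d_o. This is an unbiased comparison of the two programmes for any f, and it equals d_c when f = 1.

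**Dilution under hypothesis 4.** This is an illustration only, and the verdict does not rest on it. From the documents: 320 patients and the margin of 1.1. Assumed: 320/2 = 160 per arm, complete follow-up, 30% mortality under SOC for all patients, and a two-sided 95% interval on the log odds ratio (OR).

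- True OR 1.0: SE = √[2 × (1/48 + 1/112)] = 0.244. The pass probability is Φ(ln 1.1/0.244 − 1.96) = Φ(−1.57) = 5.8%.
- True OR 1.5 in cisplatin patients and 1.0 in others: mortality in cisplatin patients under COMP-VA is 0.391. With f = 0.5 the COMP-VA risk is (0.391 + 0.300)/2 = 0.346 and the pooled OR is (0.346/0.654)/(0.3/0.7) = 1.23.

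| f | Pooled OR | Pass probability |
|---|---|---|
| 1 | 1.50 | 0.05% |
| 0.75 | 1.36 | 0.21% |
| 0.5 | 1.23 | 0.74% |

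Dilution does raise the chance of a false pass. However, as f falls towards 0 the chance approaches the 5.8% found at an OR of 1.0, so under these assumptions it stays small. The strict margin, set against this sample size, is what limits it.

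**The case for a change.** The best case for a change is that nothing in either document states a cisplatin requirement, so its presence is inferred. A safety conclusion should say whom it covers, and one added sentence would cost almost nothing. If entry was broad, a supportive analysis in patients with planned cisplatin could be added from treatment plans that A1 says are already consulted.

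Part of this stands. The documents do not settle whether planned cisplatin was required, and a conclusion worded for cisplatin would be too narrow if it was not. But the sentence would record a fact about enrolment and alter no test. The rewording is needed only under a condition that the documents do not establish. The supportive table would correct no wrong result. Because the SAP describes its outcomes in the past tense, the table would probably have to be labelled post hoc as well. C3 collects the drug variables, so analysts can describe the treatment of the randomised patients and word the conclusions to match.

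**Conclusion.** No change to the plan is needed. The mismatch in wording is real, but it is a drafting gap: general terms in the entry text, a specific drug in two hypotheses, and a criteria list that is plainly incomplete as posted. It does not show that the wrong patients were enrolled or analysed. The analysis population, test statistics, margin and planned number of patients stay the same under either reading.

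The consequence for interpretation is zero if all randomised patients had planned cisplatin. Otherwise it depends on a share that the documents do not give, and the arm contrasts remain valid comparisons of the two monitoring programmes in the patients randomised. This rests on the tests being run by randomised arm, as SAP items 1 to 3 say and as item 4 implies by comparing COMP-VA with SOC patients.

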VA Office of Research and Development Results Record C0239-R

Title: Randomized Trial Comparison of Ototoxicity Monitoring Programs

ClinicalTrials.gov identifier: NCT02099786

Outcomes and Statistical Plan; Document Date: 9-29-17

Outcomes and Statistical Plan

Outcome Measures

The following outcomes were evaluated as a function of treatment arm.

1. **Hearing tests.** Rates of ototoxicity were evaluated using two criteria: (i) Ototoxic hearing shifts meeting the ASHA 1994 definition 20dB shift at one frequency; 10 dB shift at two consecutive frequencies or loss of response at three frequencies. (ii) Ototoxicity meeting the Cancer Institute Common Terminology Criteria for Adverse Events (CTCAE) Grade 1 or greater toxicity [hearing shift of 15-25 dB averaged at 2 contiguous test frequencies in at least one ear].
2. **Audiology rehabilitation service use.** This included: (i) service utilization to issue new hearing aids to subjects who were not hearing aid users at baseline; and (ii) technology update or hearing aid adjustment for previous hearing aid users. CPRS progress notes were monitored by the NCRAR Research Audiologist on each subject enrolled in the study in order to determine audiology rehabilitation service use for one year post-randomization. All audiology clinic visits were recorded by date and type of visit. Additionally, subjects were queried about aural rehabilitation service at each PE and interim phone calls.
3. **Quality of life measures.** Differences in the HHIA questionnaire score (or HHIE score as appropriate depending on the age of the subject) at PE 3 were evaluated.
4. **Survivorship** among subjects was also evaluated, defined as differences in rates of death during the study period.

Hypotheses to be Tested and Statistical Plan

1. *Use of COMP-VA will improve patients' hearing and quality of life outcomes without diminishing chances for survival.* Simple analysis will entail computing odds ratios and contrasting these between the COMP-VA and SOC groups. We will also fit a logistic regression model to the probability of ototoxicity (separately modeled for ASHA and CTCAE grade 1 or

greater) with randomization group assignment as predictor. *We anticipate that hearing loss progression will be less among COMP-VA subjects, meaning that, the COMP-VA group will have smaller 35 day and 1 year post-randomization hearing shifts compared to SOC patients.*

2. *We hypothesize that COMP-VA will minimize some of the adverse effects of cisplatin treatment on Veterans' hearing-related quality of life, either through treatment modifications to diminish cisplatin-induced hearing loss or effective post-chemo audiological service delivery to limit the ill-effects of any pre-existing, new or worsened communication deficit.* We will conduct a contrast of perceived hearing handicap (HHIE or HHIA questionnaire administered at 1 year post-randomization), between patients randomized to COMP-VA and SOC. We will conduct a t-test with randomization arm as the contrast to test the importance of COMP-VA on perceived quality of life outcomes.

3. *Compared with patients randomized to SOC, patients randomized to COMP-VA will use Audiology rehabilitation services at a higher rate because of their greater awareness of new, increased or pre-existing communication deficits.* To test this hypothesis, we will contrast the probability of one or more audiology clinic rehabilitation visits using logistic regression with group membership as a factor.

4. *We anticipate that cisplatin patients given the COMP-VA intervention will fair no worse than SOC patients in terms of their survival.* This component of the study is framed as a non-inferiority trial. i.e. we require sufficient evidence to reject the null hypothesis that COMP-VA patients have lower one-year survival rates than patients treated under SOC. Analysis for non-inferiority trials using survival outcomes have been described and are easily computed using logistic regression output. We will require a non-inferiority margin of no more than 1.1 mortality odds among COMP-VA patients relative to SOC patients. From an analytical

perspective this means that the upper 95% confidence bound for the fitted odds ratio must be less than 1.1 to reject the null hypothesis that COMP-VA induces extra mortality risks.

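### Does leaving the reference test for a hearing shift unnamed in SAP item 1 put the ototoxicity comparison at risk?

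*SAP*

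**What the plan says.** SAP, Hypotheses, item 1 plans odds ratios and then states: "We will also fit a logistic regression model to the probability of ototoxicity". ASHA and CTCAE grade 1 or greater are modelled separately, with arm as predictor. A following sentence expects smaller shifts under COMP-VA at 35 days and at 1 year after randomisation. Neither the reference test nor the visit supplying the follow-up threshold is named.

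Protocol A1 gives the order of testing. The first PE comes first: "Initial testing to establish inclusion in the study and to provide the first PE will be done in a quiet area". Randomisation follows. The patient is then "assigned to a study arm and is ready to receive a baseline evaluation". Section B treats PE, SOC and COMP-VA measurements as three separate groups, and A1 says patients are told at consent about the study's demands, "including the necessity for duplicate testing".

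Protocol B2, headed as general procedures for ototoxicity monitoring, has the only explicit reference rule: "Results from the baseline test will be compared to all subsequent testing for the purposes of ototoxicity detection". Set-ups differ by arm. Section C1 says "Equipment and space used for testing at the VAPORHCS Audiology clinic will be used for SOC", and B2b says "COMP-VA hearing testing is done primarily using the OtoID and/or the OtoID-Tablet and/or a standard audiometer".

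Protocol B1 calls PE 3 the final hearing session and makes the longitudinal PE depend on the date of randomisation, without giving a cut-off.

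**The concern.** A shift is a difference between two tests, so an outcome defined as a shift is incomplete until both tests are named. The documents offer two candidates for the first. One is PE 1, done before allocation and so by a procedure that cannot depend on arm. The other is the B2 baseline, done after allocation by a procedure that does. B2 is the only place that names a reference, and its wording reaches every later test.

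If PE follow-up thresholds were compared with the B2 baseline, any systematic gap between the PE set-up and the clinic or OtoID set-up would count as hearing change, by a different amount in each arm. Randomisation would not remove this, because the reference itself would be measured differently by arm. The direction cannot be known, since the PE equipment is not described.

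Three smaller gaps add to the impression of an open plan: no visit is tied to 35 days, no date decides who is due PE 3, and no criterion or time is called primary.

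**Working it through.** The plan states no power, event rate or significance level for item 1, so there is no figure to reproduce. The check is mainly of the text.

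**1. Which pairings of tests are possible?**

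| Follow-up test | Reference | Consequence |
|---|---|---|
| PE | PE 1 | Reference taken before allocation; no arm-specific reference |
| Arm's monitoring test | B2 baseline | A fixed set-up offset largely cancels within each arm |
| PE | B2 baseline | Set-up offset enters, possibly by a different amount in each arm |

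Only the third pairing produces the feared bias, and it crosses two series that the Protocol keeps apart. The second fits the SAP poorly: COMP-VA is tested at each treatment interval and one month after treatment, whereas the SAP counts 35 days and 1 year from randomisation. The first pairing matches the numbered PE series and the duplicate testing.

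**2. How large would the third pairing's bias be?** The documents fix only the criteria: 10 dB at two consecutive frequencies (ASHA) and 15 dB as the lower CTCAE limit. Everything else here is assumed: no true arm difference, 40% ototoxic with a common reference, one normal deciding shift with SD 10 to 15 dB, and an offset d in one arm only. Then rate = Φ(Φ⁻¹(0.40) + d/SD), with Φ⁻¹(0.40) = −0.253.

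- d = 5, SD 15: Φ(−0.253 + 0.333) = 0.532; OR = (0.532/0.468)/(0.40/0.60) = 1.70.
- d = 5, SD 10: Φ(−0.253 + 0.500) = 0.597; OR = 2.23.
- d = 0: OR = 1.00.

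The mechanism matters if it occurs, but no document supplies d. The Protocol requires annual calibration in both arms, with at least monthly level checks on the OtoID devices. That does not exclude room or procedure effects, but it makes a large fixed offset less likely.

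**3. The 35-day visit.** SAP Outcome Measures, item 3, takes the hearing handicap score at PE 3, and Hypotheses, item 2, takes it at 1 year, so PE 3 is the 1-year visit. With a first PE at entry, a PE 2 must lie between, and 35 days is the only other time named. This is inference, but a short one.

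**4. The PE 3 cut-off.** Protocol A1 expects 320 patients to be identified, and C3 expects 80 per year to be entered. If all 320 were randomised and follow-up stopped at last entry (both assumed), 80/320 = 25% could not reach 1 year; with 6 more months, 40/320 = 12.5%; with 12 more, none. A cut-off by randomisation date applied alike to both arms costs precision and does not favour either.

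**5. Multiplicity.** The model sentence specifies two models. At an assumed 5% per test and independence, 1 − 0.95² = 0.0975. If each were also tested at both times, 1 − 0.95⁴ = 0.185; a simulation with equally correlated tests gives 0.156 at correlation 0.5 and 0.114 at 0.8. Two criteria applied to the same thresholds are likely to be correlated, so the independent figures are upper values.

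**The case for a change.** The strongest reply is that nobody should have to infer a reference test. No passage names PE 1, the word baseline points literally to the other test, and B2 covers all later testing without exempting PEs. One sentence would settle it at no cost. The Protocol's one-month visit cannot stand in for 35 days either, being described only for COMP-VA and timed from the end of treatment. With no primary test named, a favourable result under either criterion could be presented as support for the hearing hypothesis.

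Much of this stands as description: the items are unwritten, and writing them down would make a tidier plan. What does not follow is that the analysis as planned is unsound. B2's reach is set by its heading, which is monitoring. Its baseline is arm-specific only by combining A1, B, B2a and B2b. B2b's list for COMP-VA also includes a standard audiometer, so a device contrast between arms is not certain.

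On the primary test, the 35-day and 1-year times appear in a statement of expectation that joins them, not in the model sentence. The SAP's outcome section is also already in the past tense, so a primary named now could itself be a retrospective choice. One residue remains: PE equipment is not described, so an identical PE set-up in both arms at follow-up is likely but not guaranteed.

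**Conclusion.** The concern does not call for a change. SAP item 1 leaves definitions unwritten, but the natural reading, both criteria scored from PE thresholds against PE 1, has no arm-specific reference and gives a fair comparison. Bias would require analysts to compare PE follow-up with the monitoring baseline. Its size cannot be taken from the documents, and the odds ratios of 1.70 to 2.23 for a 5 dB offset rest wholly on assumed inputs.

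The other gaps are minor. PE 3 can be placed at 1 year from the SAP itself, a date-based cut-off mainly costs precision, and the two stated models carry at most 9.75% family-wise error under independence at an assumed 5% per test. This conclusion rests on PEs being done the same way in both arms, which B1's single description of the procedure supports but does not prove. It is a gap that analysts would be expected to fill sensibly.
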